## 2. LIST OF ABBREVIATIONS

Abbreviation	Definition
5-ASA	5-aminosalicylic acid
AE	adverse event
ATC	anatomic therapeutic chemical classification system
B-hb	blood hemoglobin
B-leuk	blood leukocytes
B-ly	blood lymphocytes
B-neutr	blood neutrophiles
B-thromb	blood thrombocytes
BMI	body mass index
CRO	clinical research organization
eDMT	electronic data mining tool
EHR	electronic health record
EIM	extraintestinal manifestations
ERVA	erityisvastuualue
f-calpro	fecal calprotectin
FPFV	first patient first visit
GPP	good pharmacoepidemiology practices
HUS	Helsinki University Hospital
IBD	inflammatory bowel disease
ICD-10	International Statistical Classification of Diseases and Related Health Problems 10th revision

Abbreviation	Definition
ICMJE	International Committee of Medical Journal Editors
IEC	Independent Ethics Committee
IRB	Institutional Review Board
IPAA	ileal pouch-anal anastomosis
JAK	Janus kinase
LPLV	last patient last visit
NI	non-interventional
P-CRP	plasma C-reactive protein
P-alb	plasma albumin
pMayo	partial Mayo
QC	quality control
QoL	quality of life
RCT	randomized controlled trial
RWE	real-world evidence
SAP	statistical analysis plan
STAT	signal transducers and activators of transcription
TyK2	tyrosine kinase 2
UC	ulcerative colitis

#### 4. AMENDMENTS AND UPDATES

None.

#### 5. MILESTONES

Milestone	Planned date
Start of data collection	01 December 2021
End of data collection	30 May 2022
Final study report	01 May 2023

#### 6. RATIONALE AND BACKGROUND

Inflammatory bowel diseases (IBD) is an umbrella term used to describe disorders that involve chronic inflammation of the digestive tract. IBD includes ulcerative colitis (UC) and Crohn's disease. More than 50,000 Finns suffer from IBD¹ with approximately 2,000 new cases diagnosed each year.² UC is a chronic, relapsing systemic disease that mainly affects the gastrointestinal tract, resulting in acute and chronic intestinal inflammation. It is characterized by inflammation in the large bowel (colon). Typical symptoms include blood in stool, diarrhea, urgency, and fatigue, and often the disease has substantial consequences for work participation and sick leave. The annual incidence of UC in Finland is about 25 new cases per 100,000 inhabitants. The prevalence is estimated at 550/100,000 inhabitants.³ Based on data from the Social Insurance Institution of Finland, the incidence of UC in Finland between 2000–2007 is 2.5–3 times higher than that of Crohn's disease.⁴ The steady increase in the incidence of UC in Finland from the beginning of the 21st century to 2007 was demonstrated in a registry study of Social Insurance Institution of Finland compensation conducted by Jussila et al.⁵

Tofacitinib is an oral Janus kinase (JAK) inhibitor indicated for the treatment of several immune-mediated diseases including UC. JAKs are intracellular enzymes that transmit signals arising from cytokine or growth factor-receptor interactions on the cellular membrane to influence cellular processes of hematopoiesis and immune cell function. Within the signaling pathway, JAKs phosphorylate and activate signal transducers and activators of transcription (STATs) which modulate intracellular activity including gene expression. Tofacitinib modulates the signaling pathway at the point of JAKs, preventing the phosphorylation and activation of STATs. JAK enzymes transmit cytokine signaling through pairing of JAKs (eg, JAK1/JAK3, JAK1/JAK2, JAK1/tyrosine kinase 2 (TyK2), JAK2/JAK2). To facitinib inhibited the in vitro activities in particular of JAK1/JAK3. However, the relevance of specific JAK combinations to therapeutic effectiveness is largely unknown. The efficacy and safety of tofacitinib has been demonstrated as induction and maintenance therapy in 3 Phase 3, randomized, placebo-controlled trials in patients with moderate to severe UC.8-10 However, the study design and procedures in the randomized controlled trial (RCT) may not always reflect clinical practice and treatment patterns. Thus, it is of interest to clinicians, patients, and taxpayers to describe outcomes in the environment where the drug will be used.

Real world evidence (RWE) has become increasingly important in providing additional evidence of treatment effectiveness in clinical practice. RWE data for tofacitinib has been published for rheumatoid arthritis and an overview of these data has recently been provided while currently the primary sources of data for tofacitinib in UC patients is from the clinical development program including induction, maintenance, and long term extension studies in controlled patient populations. 10

The use of observational data will allow for the generation of data on the induction, maintenance, and effectiveness of tofacitinib outside the confines of the RCT. Examples of additional data that can be collected using the non-interventional, registry data collection includes fecal calprotectin levels - a predictor of clinical and endoscopic outcomes, extraintestinal manifestations - conditions often observed in patients with IBD and dose changes outside of the construct of the clinical trial setting.

The aim of UC treatment is to achieve remission, improve quality of life (QoL) and avoid complications from the disease including surgeries and hospital admissions as well as side-effects from long-term corticosteroid use. Despite existing treatment with mesalazine, immunomodulators and biologics, severe disease and complications are common in UC. Hence, additional treatments including those with different new modes/mechanisms of actions are needed.

### 7. RESEARCH QUESTION AND OBJECTIVES

The objective of this study is to describe and evaluate real-world data of tofacitinib for the treatment of UC in Finland in terms of clinical outcomes, treatment lines, and to identify the key characteristics of the patients treated with tofacitinib.

#### 7.1. Definitions

Active disease:

• An endoscopic Mayo sub-score  $^{12}$  of  $\geq 2$  or fecal-calprotectin (f-calpro)  $\geq 250$  mg/kg.

#### Clinical response:

- A full Mayo score  $^{12}$  decrease of  $\geq 3$  points and a decrease of  $\geq 30\%$  from baseline, with a decrease of  $\geq 1$  point on the rectal bleeding sub score or an absolute rectal bleeding score of  $\leq 1$ .
- A partial Mayo score (ie, Mayo score without endoscopic assessment) decrease of ≥2 points and reduction of at least 25% in partial Mayo (pMayo) score from baseline with an accompanying decrease in rectal bleeding sub score of ≥1 point or absolute rectal bleeding sub score of ≤1.

#### Clinical remission:

- A full Mayo score of  $\leq$ 2 points with no individual sub score exceeding 1 point, with rectal bleeding sub-score of 0.
- A pMayo score <2 points with rectal bleeding sub-score of 0.

## 7.2. Primary Objective

#### 7.2.1. To Characterize the UC Patient Group Treated with Tofacitinib.

- a. Patient demographics at tofacitinib treatment initiation: age, gender, weight, height, smoking status, body mass index (BMI), treating hospital.
- b. Disease characteristics: age at diagnosis, duration of disease, and extent of colonic involvement according to the Montreal classification: E1 (ulcerative proctitis), E2 (left sided, distal colitis), E3 (pancolitis).
- c. Disease severity as assessed by Mayo score and f-calpro at the initiation of tofacitinib use.
- d. Laboratory results for biochemical inflammatory markers plasma C-reactive protein (P-CRP), blood thrombocytes (B-thromb), plasma albumin (P-alb), blood leukocytes (B-leuk), blood lymphocytes (B-ly), blood neutrophiles (B-neutr), blood hemoglobin (B-hb) and f-calpro at the start of tofacitinib treatment (baseline data).
- e. Endoscopic findings including histology at the start of tofacitinib treatment (baseline data).

#### 7.3. Secondary objectives

#### 7.3.1. To Assess the Real-world Effectiveness of Tofacitinib.

- a. Proportion of patients who are taking to facitinib at week 8, 16, 24 and 52.
- b. To assess rates of clinical remission defined by a full or partial Mayo score at week 8, 16, 24 and 52.
- c. To assess rates of clinical response defined by a full or partial Mayo score at week 8, 16, 24 and 52.
- d. Proportion of patients in steroid-free clinical remission at weeks 8, 16, 24, and 52 as defined by full or partial Mayo who did not require any corticosteroid treatment during the period ≥4 weeks prior to the visit (for all patients and for those treated with corticosteroids at baseline).
- e. Proportion of patients reaching clinical response as defined by full or partial Mayo score at week 8, 16, 24 and 52.

- f. Time to response as assessed by a decrease as defined by full or partial Mayo score.
- g. Proportion of responders defined by a f-calpro reduction of  $\geq 50\%$ ,  $\geq 75\%$  or  $\geq 90\%$  at week 8, 16, 24 and 52 compared to baseline.
- h. Proportion of patients reaching f-calpro below 250 mg/kg at week 8, 16, 24 and 52 of those that had f-calprotectin above 250 mg/kg at baseline and change from baseline in f-calpro at week 8, 16, 24 and 52.
- i. Proportion of patients in sustained remission (pMayo and full Mayo score) from week 8 to week 16, 24 and 52.
- j. Proportion of patients in sustained remission (pMayo and full Mayo score) from week 16 to week 24 and 52.
- k. Proportion of patients in sustained steroid free remission (pMayo and full Mayo score) at week 16 to 24 and 52 (for all patients and for those treated with corticosteroids at baseline).
- 1. Change in partial and full Mayo score at weeks 8/16/24/52.
- m. Proportion of patients in sustained endoscopic remission (sub score = 0), mucosal healing (sub score 0-1) or endoscopic response (sub score reduction from baseline of ≥1) from week 8 to week 16, 24 and 52.
- n. Proportion of patients in physician assessed histological remission determined as inactive disease, or normal histology, and change from baseline in histology assessment (0= normal histology, 1= inactive disease and 2 = active disease) at week 8/16/24/52.
- o. Proportion of patients in sustained steroid free remission (pMayo and full Mayo score) (for all patients and for those treated with corticosteroids at baseline) and endoscopic remission (sub score = 0), mucosal healing (sub score 0-1) or endoscopic response (sub score reduction from baseline of ≥1) from week 8 to week 16, 24 and 52.
- p. Comparison of response and remission (pMayo and full Mayo score) based on the extent of colonic involvement.
- q. Proportion of patients with corticosteroid tapering at weeks 8/16/24/52 and their tapering rates and doses.
- r. Proportion of patients with improvement in stool frequency sub score of 1 or more points and change from baseline in stool frequency sub score at week 8, 16, 24 and 52.

- s. Proportion of patients with improvement in rectal bleeding sub score of 1 or more points and change from baseline in rectal bleeding sub score at week 8, 16, 24 and 52.
- t. Proportion of patients reaching normal P-CRP levels (below 4mg/L) and change from baseline in P-CRP levels at week 8/16/24/52.
- u. Proportion of patients reaching normal B-hb levels (men: 134–167 g/L, women: 117–155 g/L) and change from baseline in B-hb levels at week 8/16/24/52.
- v. Proportion of patients reaching normal B-leuk levels (3.4-8.2 x 10^9/L) and change from baseline in B-leuk levels at week 8/16/24/52.
- w. Proportion of patients reaching normal B-Thromb (150–360 x 10^9/L) and change from baseline in B-Thromb levels at week 8/16/24/52.
- x. Proportion of patients reaching normal B-ly  $(1.3-3.6 \times 10^9/L)$  and change from baseline in B-ly levels at week 8/16/24/52.
- y. Proportion of patients reaching normal B-neutr (1.5-6.7 x 10^9/L) and change from baseline in B-neutr levels at week 8/16/24/52.
- z. Proportion of patients reaching normal P-alb (18-39 years: 36-48 g/L, 40-69 years: 36-45 g/L, 70 years and over: 34-45 g/L) and change from baseline in P-alb levels at week 8/16/24/52.
- aa. Proportion of patients with extended tofacitinib induction dose (additional 8 weeks with 10mg).
- bb. Real-world dosing of tofacitinib, eg, usage of a higher dose (10 mg) as maintenance therapy.
- cc. Survival without drug discontinuation, colectomy or UC-related hospitalization (using time to event analysis).

#### 7.3.2. To Assess Treatment Lines Prior to Tofacitinib Treatment.

a. Number and type of previous UC treatments.

CCI		
CCI		

[figure not shown]
#### 8. RESEARCH METHODS

#### 8.1. Study Design

This is a retrospective non-interventional multicenter patient chart data study collecting real world data of tofacitinib treated patients with UC from 21 Finnish hospital district and Helsinki city hospital (included in "hospital districts" hence forward for the purpose of this protocol) databases and for whom data is available. Real-world data through health care registers is an excellent means to understand the tofacitinib treatment and use landscape in Finland.

The main purpose is to characterize the patient population receiving to facitinib, their demographics and clinical characteristics. Patient characteristics before and after the use of to facitinib will be determined for all patients. If possible, depending on patient numbers from different areas, regional differences will also be analyzed.

Figure 1. Schematic View of Study Flow

[figure not shown]
#### 8.2. Setting

The target population for this study is adult ulcerative colitis patients who were prescribed tofacitinib. Estimated number of patients in this study is 100-150, with the aim of covering all ulcerative colitis patients in Finland treated with tofacitinib. The main inclusion criteria are a diagnosis of ulcerative colitis (ICD-10: K51) between January 2010 and December 2021 and treatment with tofacitinib. The main exclusion criteria are age under 18 years, use of tofacitinib before national reimbursement decision on 01 March 2019 and history of panproctocolectomy, ileal pouch-anal anastomosis (IPAA) or ileostomy.

The data collected has been generated as part of standard clinical care, treatment, and follow-up of ulcerative colitis patients. In accordance with the Finnish Act on Secondary Use of Health and Social Data 552/2019 (in Finnish: Laki sosiaali- ja terveystietojen toissijaisesta käytöstä), health registry data can be processed in scientific studies without patient consent. The purpose of this act is to establish conditions for the effective and secure processing of, and access to, personal health and social data for certain secondary purposes, such as research and statistics, innovation and development, knowledge management, teaching and authority planning. Thus, the Secondary Act creates a clear legal basis for the use of such registered data for research and innovation related to, for example, the health and well-being of citizens, the prevention of disease and the development of new treatment methods. This relatively new legislation is also a welcome unification of the fragmented Finnish national rules regarding the use of healthcare and social welfare data. In addition, it takes into consideration current data protection requirements.

The data will be collected by data miners in all hospital districts across Finland and entered into an electronic data mining tool (eDMT) which will be designed for the study in collaboration with Finnish clinicians. The data will be used to investigate and describe the patient population, treatment strategies and disease development.

Figure 2. Study Timeline

FPFV= First patient first visit, LPLV= Last patient last visit.

Please note that dates are subject to change depending on how long permit process with Findata takes.

#### 8.2.1. Inclusion Criteria

Patients must meet all of the following inclusion criteria to be eligible for inclusion in the study:

- 1. Xeljanz (tofacitinib) usage for ulcerative colitis.
- 2. Diagnosis of ulcerative colitis (ICD-10: K51.0, K51.1, K51.2, K51.3, K51.5, K51.8, K51.9) between January 2010 and December 2021 (incident or prevalent).

#### 8.2.2. Exclusion Criteria

Patients meeting any of the following criteria will not be included in the study:

- 1. Age <18 years at the start of tofacitinib use.
- 2. Use of tofacitinib before reimbursement (01 Mar 2019).
- 3. < 8 weeks of treatment with tofacitinib at the start of data mining.
- 4. History of panproctocolectomy, IPAA or ileostomy.

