## **Table 1. Variables Collected in This Study**

Data source for all variables is the eDMT based on patient charts.

Variable	Role	Operational definition
Tofacitinib start date	Index Inclusion criteria 1 Exclusion criteria 2	First day on tofacitinib administration
Date of birth	Exclusion criteria 1 Primary objective 7.2.1.a	Age will be defined as of index date
History of bowel surgery	Exclusion criteria 4	Panproctocolectomy, IPAA or ileostomy
Gender	Primary objective 7.2.1.a	Male/female
Smoking status	Primary objective 7.2.1.a	Current/ex-smoker/non- smoker/unknown
BMI	Primary objective 7.2.1.a	Derived from weight and height
Weight	Primary objective 7.2.1.a	kg
Height	Primary objective 7.2.1.a	cm
Treating hospital	Primary objective 7.2.1.a	name of treating hospital
Mayo score	Primary objective 7.2.1.c Secondary objectives 7.3.1.b, 7.3.1.c, 7.3.1.d, 7.3.1.e, 7.3.1.f, 7.3.1.i, 7.3.1.j, 7.3.1.k, 7.3.1.l, 7.3.1.o, 7.3.1.p.	Sum of "endoscopic findings", "stool frequency", Doctors assessment of disease severity" and "rectal bleeding"
First UC diagnose	Primary objective 7.2.1.b Inclusion criteria 2	Date
Extent of colonic involvement	Primary objective 7.2.1.b	Montreal classification: E1, E2 or E3
Endoscopic findings	Primary objective 7.2.1.c and 7.2.1.e. Secondary objective 7.3.1.m	0-3 (mayo score component)
Histological activity	Primary objective 7.2.1.e Secondary objective 7.3.1.n	Active disease (2) / inactive disease (1) /normal histology (0) / not determined
Clinician's assessment of disease severity	Primary objective 7.2.1.c	0-3 (mayo score component)

Variable	Role	Operational definition
Stool frequency	Primary objective 7.2.1.c Secondary objectives 7.3.1.r	0-3 (mayo score component)
Rectal bleeding	Primary objective 7.2.1.c Secondary objective 7.3.1.s	0-3 (mayo score component)
Fecal calprotectin	Primary objective 7.2.1.d, Secondary objectives 7.3.1.g and 7.3.1.h.	mg/kg
Plasma CRP	Primary objective 7.2.1.d Secondary objective 7.3.1.t	mg/L
Blood hemoglobin	Primary objective 7.2.1.d, Secondary objective 7.3.1.u	g/L
Blood leukocytes	Primary objective 7.2.1.d Secondary objective 7.3.1.v	cells/L
Blood thrombocytes	Primary objective 7.2.1.d Secondary objective 7.3.1.w	cells/L
Blood lymphocytes	Primary objective 7.2.1.d Secondary objective 7.3.1.x	cells/L
Blood neutrophiles	Primary objective 7.2.1.d Secondary objective 7.3.1.y	cells/L
Plasma albumin	Primary objective 7.2.1.d Secondary objective 7.3.1.z	g/L

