#### 8.5. Study Size

This study is an observational study designed to provide mainly descriptive summary information. There are no hypotheses in the study. Hence sample size calculations are not applicable. The objective is to include all patients that have used to facitinib in UC in Finland. Estimated number of observations is 100-150 subjects to the timing on the data collection.

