- 1. Xeljanz (tofacitinib) usage for ulcerative colitis.
- 2. Diagnosis of ulcerative colitis (ICD-10: K51.0, K51.1, K51.2, K51.3, K51.5, K51.8, K51.9) between January 2010 and December 2021 (incident or prevalent).

Patients will be excluded if:

- 1. Age <18 years at the start of tofacitinib use.
- 2. Use of tofacitinib before reimbursement (01 Mar 2019).
- 3. < 8 weeks of treatment with to facitinib at the start of data mining.
- 4. History of panproctocolectomy, IPAA or ileostomy.

The primary variable is the first recording (date) with tofacitinib for the treatment of ulcerative colitis (ICD-10: K51). Additional variables to be collected according to the list in Table 1.

Table 1. Variables Collected in This Study

Data source for all variables is the eDMT based on patient charts.

Variable	Role	Operational definition
Tofacitinib start date	Index Inclusion criteria 1 Exclusion criteria 2	First day on tofacitinib administration
Date of birth	Exclusion criteria 1 Primary objective 7.2.1.a	Age will be defined as of index date
History of bowel surgery	Exclusion criteria 4	Panproctocolectomy, IPAA or ileostomy
Gender	Primary objective 7.2.1.a	Male/female
Smoking status	Primary objective 7.2.1.a	Current/ex-smoker/non- smoker/unknown
BMI	Primary objective 7.2.1.a	Derived from weight and height
Weight	Primary objective 7.2.1.a	kg
Height	Primary objective 7.2.1.a	ст
Treating hospital	Primary objective 7.2.1.a	name of treating hospital
Mayo score	Primary objective 7.2.1.c Secondary objectives 7.3.1.b, 7.3.1.c, 7.3.1.d, 7.3.1.e, 7.3.1.f, 7.3.1.i, 7.3.1.j, 7.3.1.k, 7.3.1.l, 7.3.1.o, 7.3.1.p.	Sum of "endoscopic findings", "stool frequency", Doctors assessment of disease severity" and "rectal bleeding"
First UC diagnose	Primary objective 7.2.1.b Inclusion criteria 2	Date
Extent of colonic involvement	Primary objective 7.2.1.b	Montreal classification: E1, E2 or E3
Endoscopic findings	Primary objective 7.2.1.c and 7.2.1.e. Secondary objective 7.3.1.m	0-3 (mayo score component)

Variable	Role	Operational definition
Histological activity	Primary objective 7.2.1.e Secondary objective 7.3.1.n	Active disease (2) / inactive disease (1) /normal histology (0) / not determined
Clinician's assessment of disease severity	Primary objective 7.2.1.c	0-3 (mayo score component)
Stool frequency	Primary objective 7.2.1.c Secondary objectives 7.3.1.r	0-3 (mayo score component)
Rectal bleeding	Primary objective 7.2.1.c Secondary objective 7.3.1.s	0-3 (mayo score component)

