4 ANALYSIS SETS/POPULATIONS

4.1 FULL ANALYSIS SET

Full analysis set includes all patients fulfilling inclusion criteria, and not excluded due to exclusion criteria.

- 1. Xeljanz® (tofacitinib) usage for ulcerative colitis.
- 2. Diagnosis of ulcerative colitis (ICD-10: K51.0, K51.1, K51.2, K51.3, K51.5, K51.8, K51.9) between January 2010 and December 2021 (incident or prevalent).

Patients will be excluded if:

- 1. Age <18 years at the start of tofacitinib use.
- 2. Use of tofacitinib before reimbursement (01 Mar 2019).
- 3. < 8 weeks of treatment with to facitinib at the start of data mining.
- 4. History of panproctocolectomy, IPAA or ileostomy.

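### Exclusion criterion 3 is worded as weeks of treatment; read literally, it removes patients who stopped before week 8 from the only analysis set

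*Protocol*

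**What the plan says.** Exclusion criterion 3 in protocol 8.2.2 reads "< 8 weeks of treatment with tofacitinib at the start of data mining". SAP 2.1 and SAP 4.1 carry the same rule. SAP 4.1 then defines the population: "Full analysis set includes all patients fulfilling inclusion criteria, and not excluded due to exclusion criteria". Sections 4.2 and 4.3 are marked not applicable, so this is the only analysis set.

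The stated aim is complete coverage. Protocol 8.2 describes the study "with the aim of covering all ulcerative colitis patients in Finland treated with tofacitinib", and protocol 8.5 says "The objective is to include all patients that have used to facitinib in UC in Finland". Protocol 8.9 names this coverage as the main strength and lists no selection on treatment duration among the limitations.

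Several secondary analyses count discontinuation from the first dose:
- Objective a is "Proportion of patients who are taking to facitinib at week 8, 16, 24 and 52". SAP 7.2 treats patients marked as off treatment before a timepoint as discontinued, and reports the proportion among patients not censored.
- Objective f (time to response) has discontinuation as the competing event, with the clock starting at index.
- Objective cc has discontinuation as a component of the composite, also timed from index.
- Protocol 8.7 plans time-to-event models for persistence.

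Table 1 in both documents gives the role of the tofacitinib start date as "Index Inclusion criteria 1 Exclusion criteria 2". No row is linked to criterion 3.

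**The concern.** The criterion counts weeks of treatment, not weeks since the first dose. Take a patient who started in June 2019 and stopped for good at week 5. On any later date that patient has fewer than 8 weeks of treatment and is excluded. Inclusion then depends on something that happens after time zero, and that something is itself a reported outcome.

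Three results are at stake under this reading:
- Week-8 persistence carries no information, and later persistence is overstated.
- The first 8 weeks of the discontinuation curves in f, cc and the persistence models are nearly empty of discontinuations. UC-related hospitalization in cc can still occur there.
- The baseline description, which is the primary objective, covers patients treated for at least 8 weeks and not all starters.

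Reporting the proportion of missing values would not reveal any of this, because the excluded patients are not in the data set.

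**Working it through.** The plan gives no figure to reproduce. Protocol 8.5 says sample size calculations do not apply, and 100-150 is an expected count. The check is what the literal rule does to the estimates, compared with a rule based on time since start.

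**Inputs from the documents.** Earliest eligible start: 01 March 2019 (protocol 8.2.2). Planned start of data collection: 01 December 2021 (protocol section 5), taken as the start of data mining; protocol 8.2 notes that dates may change. Expected size: 100-150.

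**Assumptions, not in the documents.** q is the share of starters who stop for good before week 8: 5, 10 or 20%. S is true persistence among all starters at a later timepoint: 50%, with 70% as a second value. Both serve only to show the range.

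**Week-8 persistence (objective a).** Literal: about 100%, whatever q is. Time since start, no stopper censored: 1 - q = 95, 90 or 80%.

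**Later persistence.** Early stoppers are off treatment later, so removing them shrinks only the denominator. The literal rule reports S/(1 - q):

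| q | Literal, S = 50% | Time since start | Difference (points) |
|---|---|---|---|
| 5% | 0.50/0.95 = 52.6% | 50.0% | 2.6 |
| 10% | 0.50/0.90 = 55.6% | 50.0% | 5.6 |
| 20% | 0.50/0.80 = 62.5% | 50.0% | 12.5 |

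These differences are not a ceiling. With S = 70% and q = 20%, 0.70/0.80 = 87.5%, a difference of 17.5 points.

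**Effect of the censoring rule.** SAP 7.1 censors after the last contact, and objective a counts only patients not censored.
- If every early stopper has left follow-up by the timepoint and nobody else has, both readings give S/(1 - q), and the criterion adds nothing.
- If half of all stoppers, early and late, lack a record, time since start gives 0.50/(0.50 + 0.25) = 66.7%. The literal rule gives 0.50/[0.50 + 0.5(1 - q - 0.50)] = 69.0, 71.4 or 76.9%. The differences are 2.3, 4.8 and 10.3 points.

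**Response and remission.** If all patients stay in follow-up, the overstatement is q times the difference in rates between continuers and early stoppers. With assumed rates of 50% and 0%, that is 2.5, 5.0 or 10.0 points. It is zero if the rates are equal or if early stoppers are no longer in follow-up. For the sustained endpoints (i, j, k, m, o), SAP 7.2 selects patients already in remission, so they are largely unaffected.

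**Patients removed by the literal rule, q = 5 to 20%.** If 100-150 counts all starters: 100 × 0.05 = 5 to 150 × 0.20 = 30. If it counts those included, n × q/(1 - q): 100 × 0.05/0.95 = 5.3 to 150 × 0.20/0.80 = 37.5.

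**What time since start would remove.** Only starts after 06 October 2021, 56 days before 01 December 2021. From 01 March 2019 the window is 1006 days, so 56/1006 = 5.6% if starts are evenly spread (assumption).

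**The case against.** The best defence is that the criterion was never meant literally. Tying it to the start of data mining has little purpose in a pure duration rule but a clear one in a minimum look-back rule. The coverage aim, the week-8 persistence endpoint and the SAP rule for discontinued patients point the same way. So does the short list in protocol 8.2 ("The main exclusion criteria are age under 18 years, use of tofacitinib before national reimbursement decision on 01 March 2019", then bowel surgery), which omits criterion 3. This stands as evidence of intent, but a reader has to assemble it from several sections, and neither document says that early stoppers are kept.

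The harm also depends on who applies the rule, which the documents do not say. Start date and treatment status are both collected, so if the rule is applied to the pooled data, either reading can be implemented there. If data miners screen on it before abstraction, excluded charts are not recoverable and districts may read it differently.

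Two stronger inferences fail. A reader might take the absent Table 1 link as proof that criterion 3 was left undefined. It is weak evidence, because other links are missing too: colonic extent is not linked to 7.3.1.p, concomitant corticosteroids are not linked to d, k or o, and tofacitinib dose is not linked to cc. A reader might also infer that no discontinuation at all can appear before week 8. The criterion does not say whether the 8 weeks are cumulative or continuous, so a patient who stops, restarts and reaches 8 weeks may be kept and contribute an early discontinuation.

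The study is descriptive and tests no hypotheses. That limits the consequences, but persistence is itself one of the descriptive results.

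**Conclusion.** The wording is defective and worth correcting before data mining. As written, criterion 3 selects on treatment duration and defines the only analysis set, which conflicts with the coverage aim and with the endpoints that count discontinuation from the first dose.

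Under the literal reading, week-8 persistence is about 100% by construction. Later persistence is inflated by the factor 1/(1 - q) when no stoppers are lost to censoring: 2.6, 5.6 or 12.5 points at the assumed S of 50% and q of 5, 10 or 20%. The inflation is larger at higher S and shrinks, down to zero, if early stoppers would be censored anyway. The documents give neither q nor S, and they do not allow the shift in the cc median to be fixed.

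A reader might go further and conclude that the sponsor intends to exclude early stoppers, or that all effectiveness results are biased upward. The documents support neither. The intent is more likely time since start, which causes no such distortion. Response and remission are inflated only if early stoppers did worse and remain in follow-up.

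**What to change.** Before data mining, the sponsor confirms which reading is meant.

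**If time since start:**
- Reword criterion 3 in protocol 8.2.2, SAP 2.1 and SAP 4.1 to: *Tofacitinib start date (index) less than 8 weeks before the start of data mining (one study-wide date), regardless of later discontinuation.*
- Add exclusion criterion 3 to the role of the start-date row of Table 1 in both documents.
- State in the SAP that patients recorded as off treatment stay in the objective a denominator as discontinued at later timepoints. SAP 7.2 already classes them as discontinued, but the censoring rule in 7.1 could otherwise remove the same patients again.

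**If treatment duration:** report the number excluded, limit conclusions to patients treated for at least 8 weeks, and do not present week-8 persistence or index-based time to discontinuation as applying to all starters.

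**Cost.** For time since start: one line in three places, one entry in each Table 1 and one SAP sentence. If miners would have screened literally, there are about 5 to 30 more charts (100-150 as all starters) or 5 to 38 (100-150 as those included) at the assumed q of 5 to 20%. Reported persistence may also be less favourable.
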